#### 8.2.1.4. Pharmacokinetics

##### 8.2.1.4.1. Pharmacokinetic (PK) Analysis Set

The primary analysis set for general PK analyses is defined as the PK analysis set, which will include all subjects who (1) are randomized into the study, (2) have received at least 1 dose of GS-9883/F/TAF, and (3) have at least 1 non missing PK concentration data for any analyte of interest reported by the PK lab.

### 8.3. Data Handling Conventions

HIV-1 RNA results of 'No HIV-1 RNA detected' and "< 20 cp/mL HIV-1 RNA Detected" will be imputed as 19 copies/mL for analysis purpose. Laboratory data that are continuous in nature but are less than the lower limit of quantitation or above the upper limit of quantitation will be imputed to the value of the lower or upper limit plus or minus one significant digit, respectively (e.g., if the result of a continuous laboratory test is < 20, a value of 19 will be assigned).

Missing data can have an impact upon the interpretation of the trial data. In general, values for missing data will not be imputed. However, a missing pre-treatment laboratory result would be treated as normal (ie, no toxicity grade) for the laboratory abnormality summary.

All available data for subjects that do not complete the study will be included in data listings.

## **8.4. Demographic Data and Baseline Characteristics**

Demographic and baseline characteristics will be summarized using standard descriptive methods including sample size, mean, SD, median, Q1, Q3, minimum, and maximum for continuous variables and frequency and percentages for categorical variables.

Demographic data will include race, ethnicity, and age.

Baseline characteristics will include body weight, height, body mass index, eGFR, HIV-1 infection, and enrollment distribution will be summarized.

For categorical demographic and baseline characteristics, the Cochran–Mantel–Haenszel (CMH) test will be used to compare treatment groups. For continuous demographic and baseline characteristics, the Wilcoxon rank sum test will be used to compare treatment groups.

## **8.5. Efficacy Analysis**

### **8.5.1. Primary Analysis**

The primary efficacy endpoint is the proportion of subjects with HIV-1 RNA  $\geq 50$  copies/mL at Week 48 as determined by the US FDA-defined snapshot algorithm. The primary analysis of the efficacy endpoint will be based on the FAS.

#### **8.5.1.1. US FDA-defined Snapshot Algorithm**

The analysis window at Week 48 is defined as from Study Day 295 to Study Day 378, inclusive. All HIV-1 RNA data collected on-treatment (ie, including data collected up to 1 day after the last dose date of study drug) will be used in the snapshot algorithm. Virologic outcome will be defined as the following categories:

- **HIV-1 RNA < 50 copies/mL:** this includes subjects who have the last available on-treatment HIV-1 RNA < 50 copies/mL in the Week 48 analysis window
- **HIV-1 RNA  $\geq 50$  copies/mL:** this include subjects
  - a) Who have the last available on-treatment HIV-1 RNA  $\geq 50$  copies/mL in the Week 48 analysis window, or
  - b) Who do not have on-treatment HIV-1 RNA data in the Week 48 analysis window and
    - 1) Who discontinue study drug prior to or in the Week 48 analysis window due to lack of efficacy, or
    - 2) Who discontinue study drug prior to or in the Week 48 analysis window due to reasons other than lack of efficacy and have the last available on-treatment HIV-1 RNA  $\geq 50$  copies/mL

- **No Virologic Data in the Week 48 Analysis Window:** this includes subjects who do not have on-treatment HIV-1 RNA data in the Week 48 analysis window because of the following:
  - a) Discontinuation of study drug prior to or in the Week 48 analysis window due to reasons other than lack of efficacy and the last available on-treatment HIV-1 RNA is < 50 copies/mL or,
  - b) Missing data during the window but on study drug

#### 8.5.1.2. Analysis of Primary Efficacy Endpoint

The null hypothesis is that the proportion of subjects with HIV-1 RNA  $\geq$  50 copies/mL at Week 48 in the GS-9883/F/TAF group is at least 4% higher than that in the SBR group; the alternative hypothesis is that the proportion of subjects with HIV-1 RNA  $\geq$  50 copies/mL in the GS-9883/F/TAF group is less than 4% higher than that in the SBR group.

Non-inferiority will be assessed using the conventional confidence interval (CI) approach. The point estimate of treatment difference (GS-9883/F/TAF – SBR) and the associated 2-sided 95% CI will be constructed based on the exact method.

It will be concluded that GS-9883/F/TAF is non-inferior to E/C/F/TAF if the upper bound of the 2-sided 95% CI of the difference between treatment groups (GS-9883/F/TAF – SBR) in the percentage of subjects with HIV-1 RNA  $\geq$  50 copies/mL is less than 4% (ie, a margin of 4% is applied to non-inferiority assessment).

If non-inferiority of GS-9883/F/TAF to SBR is established, the upper bound of the 95% CI will be compared to 0; if the upper bound of the 95% CI is less than 0, superiority of GS-9883/F/TAF over SBR will be established.

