### 1.2.3.5. Efficacy Results

Virologic success at Week 12 and 24 was assessed using the US FDA-defined snapshot algorithm, defined as plasma HIV-1 RNA < 50 copies/mL. At Weeks 12 and 24, virologic success was high and similar between the 2 treatment groups as follows: Week 12 GS-9883+F/TAF 93.8%; DTG+F/TAF 93.9% (stratum-adjusted difference in percentages: -1.3%; 95% CI: -12.9% to 10.2%; p = 0.79); Week 24 GS-9883+F/TAF 95.4%, DTG+F/TAF 93.9% (1.0%; 95%CI: -10.7% to 12.7%; p = 0.84).

Of the 5 subjects with baseline viral load > 400,000 copies/mL, 4 had HIV-1 RNA < 50 copies/mL at Week 24, and 1 was considered a virologic failure by US FDA-defined snapshot algorithm with HIV-1 RNA of 60 copies/mL.

Following initiation of study drug, the increases from baseline in CD4 cell count were similar between treatment groups. Mean (SD) baseline CD4 cell counts were as follows: GS-9883+F/TAF 471 (190.9) cells/ $\mu$ L; DTG+F/TAF 507 (271.0) cells/ $\mu$ L; p = 0.35. The mean (SD) change in CD4 cell count from baseline to Week 12 was similar between the 2 treatment groups as follows: GS-9883+F/TAF +170 (150.0) cells/ $\mu$ L; DTG+F/TAF +173 (220.5) cells/ $\mu$ L (difference in LSM: 0; 95% CI: -76 to 76; p = 1.00). There were similar increases in the mean (SD) CD4 cell count in both treatment groups at Week 24: GS-9883/F/TAF, +189 (177.8) cells/ $\mu$ L; DTG+F/TAF, +157 (163.2) cells/ $\mu$ L (difference in LSM: 39; 95% CI: -35 to 113; p = 0.30)

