## 5. INVESTIGATIONAL MEDICINAL PRODUCTS

### 5.1. Randomization

Subjects will be assigned a screening number at the time of consent. **Randomization and Day 1 visit cannot occur until subject eligibility has been confirmed.**

Once eligibility has been confirmed and prior to or during the Day 1 visit the Investigator or designee will randomize the subject using the Interactive Web Response System (IWRS). Once a subject number has been assigned to a subject, it will not be reassigned to any other subject. The subject number assignment and randomization may be performed up to 3 days prior to the in-clinic Day 1 visit provided that all screening procedures have been completed and subject eligibility has been confirmed.

Subjects will be randomized in a 1:1 ratio to Treatment Group 1 or Treatment Group 2.

- **Treatment Group 1:** FDC of GS-9883 50 mg/emtricitabine 200 mg/tenofovir alafenamide 25 mg (GS-9883/F/TAF) administered orally, once daily, without regard to food (approximately n = 235)
- **Treatment Group 2:** Stay on baseline regimen (SBR), including E/C/F/TAF, E/C/F/TDF or ATV+RTV+FTC/TDF administered orally, once daily, with food (approximately n = 235)

The IWRS will assign study drug bottle numbers of open label FDC of GS-9883/F/TAF, open label E/C/F/TAF, open label E/C/F/TDF or open label ATV+RTV+FTC/TDF at each study visit for each subject.

Randomization will be stratified by the prior treatment regimen group (ie, E/C/F/TAF, E/C/F/TDF and ATV+RTV+FTC/TDF).

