#### 8.5.2. Secondary Analyses

The proportion of subjects with HIV-1 RNA < 50 copies/mL at Week 48 as determined by the US FDA-defined snapshot algorithm will also be evaluated. The 95% CIs will be constructed in the same manner as for the primary efficacy endpoint. However, non-inferiority will be assessed using a margin of 10%. It will be concluded that GS-9883/F/TAF is non-inferior to SBR if the lower bound of the 2-sided 95% CI of the difference between treatment groups (GS-9883/F/TAF - SBR) in the response rate is greater than -10%.

The changes from baseline in CD4+ cell count at Week 48 will be summarized by treatment using descriptive statistics. The differences in changes from baseline in CD4+ cell count between the 2 treatment groups and the associated 95% CIs will be constructed using ANOVA models, including treatment (GS-9883/F/TAF vs. SBR) as a fixed effect in the model.

In addition, missing CD4+ cell count will be imputed using Last Observation Carried Forward (LOCF) method and analyzed similarly.

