3.3. Strata and Covariates

There is no stratification for analysis.

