6. EFFICACY ANALYSES

6.1. Definition of Efficacy Endpoints

6.1.1. Primary Efficacy Endpoint

The primary efficacy endpoint is the proportion of subjects with virologic failure (HIV-1 RNA ≥ 50 copies/mL) at Week 48 as defined by the modified FDA snapshot algorithm.

The analyses of the primary efficacy endpoint were performed in the Week 48 interim analyses, and will not be repeated in the final analysis.

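### Prior regimen stratifies the randomisation but enters none of the protocol's comparative efficacy analyses, so their intervals may be slightly wider than they need be

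*Protocol*

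**What the plan says.** **Randomisation.** Protocol 5.1: "Randomization will be stratified by the prior treatment regimen group (ie, E/C/F/TAF, E/C/F/TDF and ATV+RTV+FTC/TDF". The synopsis and SAP 1.2 agree, and no other factor is named.

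**HIV-1 RNA ≥ 50 copies/mL (primary).** Protocol 8.5.1.2 says of the treatment difference that "the associated 2-sided 95% CI will be constructed based on the exact method". It does not say which exact method, and it mentions no strata.

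**HIV-1 RNA < 50 copies/mL (secondary).** Protocol 8.5.2: "The 95% CIs will be constructed in the same manner as for the primary efficacy endpoint". This endpoint has its own non-inferiority conclusion, with a 10% margin.

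**Change in CD4+ count.** Protocol 8.5.2 specifies an ANOVA "including treatment (GS-9883/F/TAF vs. SBR) as a fixed effect in the model". No other term is named.

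The protocol gives no reason for leaving the factor out and plans no stratified sensitivity analysis.

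**SAP.** Section 3.3 says "There is no stratification for analysis". However, this SAP covers only the final, descriptive all-B/F/TAF analysis (sections 2.3 and 3). Of the primary endpoint analyses, SAP 6.1.1 says that they "were performed in the Week 48 interim analyses, and will not be repeated in the final analysis". The plan that governed the Week 48 comparison is not among the documents. In the SAP that we have, prior regimen is used in analysis only for a renal subgroup, as TDF-containing against not (sections 3.4 and 7.7).

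**The concern.** The usual convention is to analyse as randomised, or to say why not. Stratified allocation removes between-stratum variation from the true sampling error of the treatment difference. An unstratified interval still counts that variation, so it is too wide whenever the strata differ in outcome.

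Sparse events are a fair reason for a simple exact interval on the primary endpoint: at the planned 2% rate, 0.02 × 235 = 4.7 events are expected per arm. That reason carries over poorly to the other two endpoints. Under Protocol 8.5.1.1, subjects without virologic data also fail to count as < 50, so that endpoint has more non-responders. CD4+ is continuous.

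The sponsor has adjusted for strata before: Protocol 1.2.3.5 reports a "stratum-adjusted difference in percentages" for the Phase 2 study.

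What is at stake is a little precision. The validity of the non-inferiority test is not in question.

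**Working it through.** **1. The plan's own figure.** Protocol 8.8 gives 235 per arm, 2% in both arms, a 4-point margin and one-sided 0.025, and states at least 87% power. With the unpooled normal approximation:

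- SE = √(2 × 0.02 × 0.98 / 235) = 0.01292
- Power = Φ(0.04 / 0.01292 − 1.96) = 87.2%

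The stated figure reproduces. The 0.00001 alpha penalty in Protocol 8.9 leaves it at 87.2%. The calculation has no strata in it.

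**2. Binary endpoints: how much narrower?** With stratum shares w and stratum rates p, and p̄ = Σwp:

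- Variance reduction R = 1 − Σw·p(1−p) / [p̄(1−p̄)]
- Narrowing of the interval = 1 − √(1 − R)
- Half-width = 1.96 × √(2·p̄(1−p̄)/235)

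The documents give neither stratum sizes nor stratum rates. Those below are assumptions, with shares of 50/40/10%.

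| Endpoint | Assumed rates | p̄ | Σw·p(1−p) | p̄(1−p̄) | R | Interval narrower by | Unstratified half-width (points) | Change (points) |
|---|---|---|---|---|---|---|---|---|
| ≥ 50 | 1.5/2/4% | 1.95% | 0.01907 | 0.01912 | 0.0027 | 0.1% | 2.5 | 0.003 |
| ≥ 50 | 1/2/6% | 1.90% | 0.01843 | 0.01864 | 0.0112 | 0.6% | 2.5 | 0.014 |
| < 50 | 96/93/88% | 94.0% | 0.05580 | 0.05640 | 0.0106 | 0.5% | 4.3 | 0.02 |
| < 50 | 97/93/80% | 93.7% | 0.05659 | 0.05903 | 0.0414 | 2.1% | 4.4 | 0.09 |

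The margins are 4 points for ≥ 50 and 10 points for < 50. The largest < 50 gain needs a 17-point spread between regimens.

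**3. Sensitivity of the ≥ 50 result.** These scenarios hold the overall rate at 2%. Power is by the same normal approximation, with the variance taken within strata.

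| Shares | Rates | Narrower by | Power |
|---|---|---|---|
| equal | 2/2/2% | 0 | 87.2% |
| equal | 1/2/3% | 0.2% | 87.3% |
| equal | 0.5/1/4.5% | 0.8% | 87.8% |
| 50/40/10% | 1/1/11% | 2.3% | 88.7% |
| 50/40/10% | 0/0/20% | 9.7% | 92.9% |

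Only the last row, with every event in a 10% stratum, gives a sizeable gain. These power figures belong to a stratified asymptotic interval, so they are not gains for the exact decision rule.

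**4. CD4+.** If prior regimen explains a share R² of the variance in change, the interval narrows by 1 − √(1 − R²). For R² of 1, 2, 5 and 10%, that is 0.5, 1.0, 2.5 and 5.1%. The shares are assumed, and the two extra degrees of freedom are ignored.

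**5. Chance imbalance.** The documents give no block size. Assume permuted blocks of 4 to 8 within strata, so that the arms differ by at most 2 to 4 subjects in a stratum. Take two strata imbalanced in opposite directions, with rates 5 to 10 points apart. The crude difference then shifts by:

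- smallest case: (2/235) × 5 = 0.04 points
- largest case: (4/235) × 10 = 0.17 points

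Both are negligible against a 4-point margin.

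**The case against.** **Precision is lost only if prior regimen is prognostic.** This stands. Everyone enrolled is already suppressed, no stratum rates are given, and with equal rates the gain is zero.

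**A reader might infer that a comparator made up of three regimens leaves the pooled difference exposed to chance differences in regimen mix.** The documents do not support this. Both arms draw from the same three strata, and prior regimen is the very factor on which allocation is balanced. Balance holds at randomisation, while the full analysis set requires a dose and the per-protocol set drops subjects later. Some residual imbalance is therefore possible, but nothing suggests that it is material.

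**A reader might infer that SAP 3.3 rules out stratification for the Week 48 comparison.** It does not, because that SAP governs a later single-treatment summary. The Week 48 plan may have included a stratified analysis or justified its absence. We cannot tell, so the point is limited to the protocol text.

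**The Phase 2 precedent is weak.** Largely so. That study stratified 98 treatment-naive subjects by screening viral load, which says little about prior regimen in suppressed patients. It shows the sponsor's practice and does not show that this factor predicts outcome.

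**One method for two closely linked snapshot endpoints is defensible, and a stratified Miettinen-Nurminen interval is asymptotic.** Both are true. Replacing the exact < 50 interval would change two things at once, and the figures above isolate only the effect of stratifying. This is a reason to label the method clearly. It does not justify ignoring the stratum in the CD4+ model, where no exactness is involved.

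**Conclusion.** The point holds as a minor improvement. The protocol's comparative efficacy analyses leave out the only stratification factor, without explanation and without a stratified supportive analysis. If prior regimen predicts outcome, the intervals are slightly too wide. The error is conservative: omitting the factor does not inflate type I error or favour a non-inferiority conclusion.

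The size is about 0.1 to 0.6% of interval width for ≥ 50, 0.5 to 2% for < 50, and 0.5 to 5% for CD4+. These ranges rest entirely on assumed stratum shares, rates and variance shares. More extreme assumptions give more, and equal strata give nothing. The case for acting is that the change is almost free, and it is strongest for CD4+ and < 50, where sparse events are less of an obstacle.

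**What to change.** In Protocol 8.5.2 and the Week 48 analysis plan:

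- **CD4+:** add prior regimen (three levels) as a fixed effect beside treatment.
- **< 50:** report a Mantel-Haenszel-weighted risk difference over prior regimen with a stratified interval. If that is the stratified Miettinen-Nurminen interval, state that it is asymptotic and not exact.
- **≥ 50:** report the same stratified estimate as a prespecified supportive analysis. Keep the exact interval as the primary decision rule.

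If the sponsor prefers to leave any of these analyses unstratified, one sentence giving the reason would do. The SAP records the Week 48 analysis as already conducted (section 2.2), so a stratified analysis that its plan did not contain would have to be labelled post hoc in this trial.

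The cost is some wording and a small amount of extra analysis. Prior regimen is already recorded, because it drives the randomisation. No new data and no change to sample size are needed.

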#### 8.5.2. Secondary Analyses

The proportion of subjects with HIV-1 RNA < 50 copies/mL at Week 48 as determined by the US FDA-defined snapshot algorithm will also be evaluated. The 95% CIs will be constructed in the same manner as for the primary efficacy endpoint. However, non-inferiority will be assessed using a margin of 10%. It will be concluded that GS-9883/F/TAF is non-inferior to SBR if the lower bound of the 2-sided 95% CI of the difference between treatment groups (GS-9883/F/TAF - SBR) in the response rate is greater than -10%.

The changes from baseline in CD4+ cell count at Week 48 will be summarized by treatment using descriptive statistics. The differences in changes from baseline in CD4+ cell count between the 2 treatment groups and the associated 95% CIs will be constructed using ANOVA models, including treatment (GS-9883/F/TAF vs. SBR) as a fixed effect in the model.

In addition, missing CD4+ cell count will be imputed using Last Observation Carried Forward (LOCF) method and analyzed similarly.

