**Statistical Methods:**

The primary analysis will consist of a non-inferiority test of switching to GS-9883/F/TAF FDC versus SBR with respect to the proportion of subjects with HIV-1 RNA  $\geq 50$  copies/mL at Week 48 as determined by the US FDA-defined snapshot algorithm. It will be concluded that GS-9883/F/TAF is non-inferior to SBR if the upper bound of the 2-sided 95% confidence interval (CI) of the difference between treatment groups (GS-9883/F/TAF – SBR) in the proportion of subjects with HIV-1 RNA  $\geq 50$  copies/mL is less than 4%; ie, a margin of 4% is applied to non-inferiority assessment. The 2-sided 95% CIs will be constructed based on the exact method.

The proportion of subjects with HIV-1 RNA  $< 50$  copies/mL at Week 48 as determined by the US FDA-defined snapshot algorithm will also be summarized. The 95% CIs will be constructed in the same manner as described for the primary efficacy endpoint.

The change from baseline in CD4+ cell count at Week 48 will be summarized by treatment using descriptive statistics. The differences and the associated 95% CIs will be constructed using Analysis of Variance (ANOVA) model, including treatment (GS-9883/F/TAF vs. SBR) as a fixed effect in the model.

Adverse events and clinical laboratory assessments will be summarized using descriptive statistics.

A total of approximately 470 HIV-1 infected women, randomized in a 1:1 ratio to 2 treatment groups (approximately 235 subjects per treatment group), achieves at least 87% power to detect a non-inferiority margin of 4% difference in the percentage of subjects with HIV-1 RNA  $\geq$  50 copies/mL at Week 48 between the 2 treatment groups.

For sample size and power computation, it is assumed that both treatment groups have 2% of subjects with HIV-1 RNA  $\geq$  50 copies/mL at Week 48 (based on the historical Gilead Genvoya® (GEN) and Stribild® (STB) studies), that a non-inferiority margin is 4%, and that the significance level of the test is at a one-sided 0.025 level.

---

This study will be conducted in accordance with the guidelines of Good Clinical Practice (GCP) including archiving of essential documents.

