### **8.8.            Sample Size**

A total of approximately 470 HIV-1 infected subjects, randomized in a 1:1 ratio to 2 treatment groups (approximately 235 subjects per treatment group), achieves at least 87% power to detect a non-inferiority margin of 4% difference in percentage of subjects with HIV-1 RNA  $\geq$  50 copies/mL at Week 48 between the 2 treatment groups. For the sample size and power computation, it is assumed that both treatment groups have 2% of subjects with HIV-1 RNA  $\geq$  50 copies/mL at Week 48 (based on the historical Gilead GEN and STB studies), that the non-inferiority margin is 4%, and that the significance level of the test is at a one-sided 0.025 level.

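### The secondary non-inferiority test on HIV-1 RNA < 50 copies/mL (margin -10%) has no condition on the primary 4% test, so the protocol as written allows a non-inferiority verdict after the primary has failed

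*Protocol*

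**What the plan says.** **Primary rule.** Protocol Section 8.5.1.2 compares the upper 95% limit of the difference "in the percentage of subjects with HIV-1 RNA" at or above 50 copies/mL with 4%: "a margin of 4% is applied to non-inferiority assessment". A conditional step follows: "If non-inferiority of GS-9883/F/TAF to SBR is established, the upper bound of the 95% CI will be compared to 0". This is the only ordering of tests in Section 8.5.

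**Secondary rule.** Section 8.5.2 turns to the proportion below 50 copies/mL. On the interval it says "The 95% CIs will be constructed in the same manner as for the primary efficacy endpoint". It then sets a margin of 10% and a conclusion: "It will be concluded that GS-9883/F/TAF is non-inferior to SBR if the lower bound of the 2-sided 95% CI" of the difference in response rate exceeds -10%. The sentence has no condition on the primary result.

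**Level.** Section 8.8 puts the primary test at one-sided 0.025: "the significance level of the test is at a one-sided 0.025 level". The secondary uses a two-sided 95% interval, so it is also at one-sided 0.025. The alpha penalty for data monitoring committee analyses in Section 8.9 applies only to the primary endpoint.

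**Synopsis.** Under Statistical Methods, the < 50 proportion "as determined by the US FDA-defined snapshot algorithm will also be summarized", with intervals built as for the primary. No 10% margin or non-inferiority conclusion appears there.

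**SAP.** Section 3.5 mentions multiplicity adjustment only for the Week 48 primary endpoint analysis. Section 6.3 plans no change to the protocol's efficacy analyses. Sections 2.3 and 6.2 limit this SAP to the final B/F/TAF-only analysis and say the snapshot comparisons were done at Week 48.

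**The concern.** Two rules end in nearly the same words, non-inferior to the comparator, with different endpoints and margins. The second is usually easier to meet and can be applied whatever the first shows. The authors wrote a condition for superiority in the section just before and none here, so a reader has no textual ground for supplying one.

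Two things are at stake. With two tests at one-sided 0.025 and no order, the chance of at least one false non-inferiority conclusion is not held at 2.5%. And if the primary fails, the protocol still supports a formal sentence that B/F/TAF is non-inferior to SBR. Only the description of the difference, not the verdict itself, says which endpoint is meant.

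**Working it through.** **Inputs from the protocol.** 235 per arm, 2% failures (HIV-1 RNA >= 50 copies/mL) assumed in both arms, margin 4%, one-sided 0.025, power at least 87% (Section 8.8); secondary margin -10% (Section 8.5.2).

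**Assumed.** The documents give no rate for the snapshot category without Week 48 data, so a range is shown. They do not name the exact method, so score tests are used for both endpoints. An exact unconditional version of the primary score test gave the same power at 2% vs 2%.

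**1. The plan's own figure.** Power = Phi(0.04 / sqrt(2 x 0.02 x 0.98 / 235) - 1.96) = Phi(0.04 / 0.012915 - 1.96) = Phi(1.137) = 87.2%. The stated figure reproduces. It concerns the primary only.

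**2. Can the two verdicts part?** Take 13/235 failures on B/F/TAF, 5/235 on SBR, and 12 without data in each arm.
- Primary: 5.53% - 2.13% = 3.40%. SE = sqrt(0.0553 x 0.9447/235 + 0.0213 x 0.9787/235) = 1.763%. Upper Wald limit = 3.40 + 1.96 x 1.763 = 6.9%. This is above 4%, so non-inferiority is not shown.
- Secondary: 210/235 - 218/235 = 89.36% - 92.77% = -3.40%. SE = sqrt(0.8936 x 0.1064/235 + 0.9277 x 0.0723/235) = 2.627%. Lower Wald limit = -3.40 - 1.96 x 2.627 = -8.6%. This is above -10%, so non-inferiority is concluded.

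Score tests give the same two verdicts.

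**3. Error rate when both nulls hold.** Both boundaries are met when failures are 6% vs 2% (difference +4%) and success differs by -10%. The no-data rate must then be 6 points higher on B/F/TAF. Simulated trinomial trials, at least 400,000 per row:

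| No data, SBR / B/F/TAF | Primary passes | Only secondary passes | At least one passes |
|---|---|---|---|
| 2% / 8% | 2.29% | 1.74% | 4.0% |
| 4% / 10% | 2.25% | 1.89% | 4.1% |
| 5% / 11% | 2.30% | 1.87% | 4.2% |
| 8% / 14% | 2.25% | 2.08% | 4.3% |
| 10% / 16% | 2.26% | 2.16% | 4.4% |

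The value for two independent tests is 1 - 0.975^2 = 4.94%. If the secondary is tested only after the primary passes, the last column falls to the primary column, about 2.3%.

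**4. How often the verdicts would diverge (not an error rate).** Failures 6% vs 2%, equal no-data rates:

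| No data, each arm | Secondary passes | Primary fails and secondary passes |
|---|---|---|
| 2% | 73% | 70% |
| 3% | 68% | 65% |
| 5% | 59% | 57% |
| 8% | 50% | 48% |

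Here the true < 50 difference is -4%, inside -10%. A secondary pass is a correct statement about its own hypothesis.

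**The case against.** **The divergence figures are not false positives.** A reader might take 48% to 70% as the rate of wrong conclusions. It is not: with success truly 4 points lower, non-inferiority at 10% is true, so the figure mostly reflects the secondary test's power. The same holds at 2% vs 2% failures, where score tests have the primary fail and the secondary pass in about 19% to 22% of trials. Both nulls are false there, and the figure mainly restates the primary's miss rate (22% with a score test, 13% by the plan's own approximation). This objection stands in full; only step 3 measures error.

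**The rule does not replace the primary.** A reader might infer a second route to the trial's main conclusion. The documents do not support that. There is one primary objective, one primary endpoint and one powered hypothesis. The -10% rule sits under secondary analyses, concerns a named secondary endpoint and refers to the response rate. It neither reverses a failed primary nor changes that test's own 0.025. This stands too, but it leaves the unqualified wording of the verdict and the missing order.

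**The operative plan may already settle it.** The Week 48 analysis plan is not supplied and could contain a sequence. So the absence of an order can be asserted of protocol Section 8.5, not of the analysis as carried out.

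**The synopsis does not contradict the body.** It says the endpoint is summarized, not that it is only summarized, and it also leaves out the superiority test. That is better read as abbreviation. It does leave the formal status of the < 50 comparison unstated there.

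**Conclusion.** The point holds for the protocol text. Section 8.5.2 attaches a formal non-inferiority conclusion to the secondary endpoint with no condition on the primary, and nothing in the supplied documents adds one. Followed as written, that verdict can be issued after the primary has failed.

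The multiplicity cost is moderate: about 4.0% to 4.4% instead of 2.5% for at least one false non-inferiority conclusion with both nulls at their boundaries. This rests on 235 per arm, score tests, and assumed no-data rates of 2% to 10% on SBR, 6 points higher on B/F/TAF. The 48% to 70% divergence at 6% vs 2% failures (equal no-data rates of 2% to 8%, assumed) shows that the question could matter in practice, and nothing more. The Week 48 plan may differ.

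**What to change.** - State in Section 8.5.2 that the -10% comparison is a formal test only once non-inferiority at 4% has been shown on the primary endpoint. Otherwise the < 50 difference and its 95% interval are descriptive.
- Word the secondary conclusion as non-inferiority on the proportion below 50 copies/mL, so that it cannot be read as the trial's overall verdict.
- State where superiority stands in the sequence. Superiority and the -10% test would both follow primary non-inferiority, each at one-sided 0.025, so they need an order between them.
- Align the Statistical Methods part of the synopsis, and confirm that the Week 48 analysis plan says the same.

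This takes two or three sentences in the protocol and a line in the synopsis. The sample size and the primary power of 87.2% by the plan's approximation do not change. The loss is that no formal secondary claim can be made if the primary fails.
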